**Table 8–1: Vital signs abnormality criteria**

Parameter	Age Range	Abnormality Criteria
Pulse Rate (beats/minute)	<6m	<100 >180
	6m - <3y	<90 >150
	3y - <12y	<60 >130
	12y - <17y	≤50 ≥120
	≥17y	≤50 and a decrease from Baseline of ≥15 ≥120 and an increase from Baseline of ≥15
Systolic Blood Pressure (mmHg)	<6m	<60 >100
	6m - <3y	<70 >120
	3y - <12y	<80 >140
	12y - <17y	<90 >160
	≥17y	≤90 and a decrease from Baseline of ≥20 ≥180 and an increase from Baseline of ≥20

**Table 8–1: Vital signs abnormality criteria**

Parameter	Age Range	Abnormality Criteria
Diastolic Blood Pressure (mmHg)	<6m	<40 >65
	6m - <3y	<45 >75
	3y - <12y	<50 >80
	12y - <17y	≤50 ≥105
	≥17y	≤50 and a decrease from Baseline of ≥15 ≥105 and an increase from Baseline of ≥15
Temperature	>1m	>101 °F (38.3 °C)
Body Weight	1m - <17y	<3% or >97% of the normal body weight growth curve ranges a based on gender and the age of subject on date of weight assessment
	≥17y	≥10% change from Baseline (an increase or a decrease)

Abbreviations: m=months, y=years. A month is defined as 28 days; a year is defined as 365.25 days.

a Source: <http://www.cdc.gov/growthcharts/>.

A subject data listing of all vital signs for study participants with an AE mapped to the PT bradycardia or sinus bradycardia will be presented.

A subject data listing of all vital sign values including body weight, height, and BMI for all study participants will be presented. A separate listing including MA vital signs values will also be presented.

#### 8.4.2 Electrocardiograms (ECGs)

Standard 12-lead ECGs (2 interpretable recordings [20 to 30 minutes apart]) will be performed throughout the study, according to the tabular schedule of study procedures.

For ECGs, Baseline will be defined as the average of all pre-dose interpretable readings. Assessments with missing time on day of first dose will be assumed pre-dose. For all post-Baseline visits, the average of all interpretable readings at the specified visit will be used for summaries.

Observed values of ECG results will be summarized for each visit and Last Visit. Change from Baseline in ECG results will be summarized for all post-Baseline visits, and Last Visit. This will be summarized overall and repeated by weight band using the levels defined in Section 3.2.10.

The number and percentage of study participants with no abnormality, an abnormal but not clinically significant finding, and a clinically significant finding, will be summarized for all visits, and Last Visit. Percentages will be relative to the number of study participants with an

ECG assessment at each visit. Study participants are counted at most once at each visit based on the worst observed outcome across all abnormalities reported at that visit.

Summaries of shifts from Baseline to post-Baseline visits, and from Baseline to Last Visit will also be provided based on the categories normal, abnormal, not clinically significant, and abnormal, clinically significant.

A listing of ECG data will be provided for all study participants with other significant TEAEs in the Cardiac and ECG Related Terms category defined in Appendix 12.2. A subject data listing of all ECG parameter values for all study participants will also be presented. Listings will include results from each recording and the average of all recordings.

The number and percentage of study participants with treatment-emergent ECG abnormalities will be presented for each post-Baseline visit and Last Visit. Abnormalities reported at an unscheduled visit will be summarized under the scheduled visit preceding the unscheduled visit (if the abnormality was not present already at the preceding scheduled visit). Treatment-emergent is defined as meeting the criteria at any post-Baseline visit during the Treatment Period (including unscheduled visits) and not meeting the same criteria during Baseline. The age at the time of visit/assessment will be used for determining abnormality criteria. The age at the time of assessment will be obtained using date of informed consent to date of visit. All ECG parameter values will be listed for study participants meeting any abnormality criteria.

Abnormality criteria to be used in the determination of ECG abnormalities are defined as follows, where increase and decrease are relative to Baseline values:

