### **3.2.3 Mapping of assessments performed at Early Termination Visit**

Safety and efficacy assessments at an Early Termination Visit (ETV) that correspond to a scheduled visit will be summarized at the scheduled visit corresponding to the ETV if the assessment was scheduled to occur at that visit. Such assessments will also be considered for Last Visit. Study participants who prematurely discontinue the study will be evaluated based on the data collected at each visit attended. For those study participants the ETV will be mapped to the next scheduled visit, ie, the assessments documented at Visit 13/ETV will be assigned to the next scheduled visit, for which the corresponding assessment is scheduled, following the last documented visit.

In particular, assessments which are done at all visits during the Treatment Period (eg, vital signs, body weight and height), will have ETVs corresponding to a scheduled visit mapped to the corresponding scheduled visit.

For study participants enrolled from sites in Japan, they are allowed to stay in the study longer than 2 years. Such study participants will have a separate ETV if they are in the study after Visit 13.

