### **3.3 Definition of Baseline values**

In general, Baseline will be defined as the last non-missing value collected prior to the first dose of LCM in the original study for rollover subjects and in SP848 for direct enrollers for safety and efficacy variables unless otherwise noted for a specific type of data. The Baseline value for seizure counts for directly enrolled study participants will be taken from the Historical Seizure Count CRF/eCRF module collected in SP848 in combination with the seizure diary data collected from the date of the Screening Visit to the day prior to the date of first dose of LCM.

For participants enrolling from EP0060 the baselines for the questionnaires will consider each EP0060 enrollment group separately, those are: ILL (Initiating intravenous lacosamide Group: not currently receiving LCM, i.e. LCM naïve), OLL (Open-label lacosamide Group: currently receiving oral LCM in open-label long term study), and RxL (Prescription lacosamide Group: currently receiving prescribed oral LCM from commercial supply, VIMPAT). For ILL group baseline will be Visit 1 from SP848, for OLL group baseline will come from SP848 using above baseline definition, and for RxL group there will be no baseline data as they were on oral LCM prior to EP0060.

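### For direct enrollers, an ECG abnormality seen only at an unscheduled visit between the first LCM dose and the first post-dose scheduled visit is assigned to a pre-dose visit and can be missing from the treatment-emergent ECG table

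*SAP*

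**What the plan says.** Section 8.4.2 sets the table's layout: "The number and percentage of study participants with treatment-emergent ECG abnormalities will be presented for each post-Baseline visit and Last Visit". It then gives the assignment rule for unscheduled ECGs: "Abnormalities reported at an unscheduled visit will be summarized under the scheduled visit preceding the unscheduled visit", with the proviso that the abnormality was not already there at that preceding visit. The definition that follows takes in unscheduled ECGs: "Treatment-emergent is defined as meeting the criteria at any post-Baseline visit during the Treatment Period (including unscheduled visits"), and it requires that the same criterion was not met at Baseline. Nothing is said about a preceding visit that falls before dosing, and no entry covers the Treatment Period as a whole.

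Two Baseline statements bear on this. Section 8.4.2 has its own: "For ECGs, Baseline will be defined as the average of all pre-dose interpretable readings". The general definition in section 3.3 reads: "Baseline will be defined as the last non-missing value collected prior to the first dose of LCM in the original study for rollover subjects", and uses the first SP848 dose for direct enrollers.

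**The concern.** The definition and the assignment rule do not fit together at the start of treatment. The definition counts an abnormality found at an unscheduled visit after dosing has begun. The rule can then place it at a visit before dosing began, and such a visit has no entry in the table. The by-visit table is the only planned count of abnormalities against the Table 8-2 criteria. At stake is whether that count includes every participant who had a treatment-emergent abnormality, including those in whom it appeared soon after LCM was started and was not seen again.

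**Working it through.** The plan gives no figure to reproduce. The check is to follow the rule through each enrollment route.

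**Inputs from the SAP**
- Assignment rule, table entries and treatment-emergent definition: section 8.4.2.
- Last Visit is the last non-missing assessment in the Treatment Period, with unscheduled ones eligible: section 3.2.6.
- Direct enrollers are screened and then start LCM; their Titration Period starts at first dose and ends the day before Visit 1: sections 2.4.1.2 and 3.2.2.
- Titration visits are scheduled visits: section 3.2.4.
- Rollover participants enter already taking LCM: section 2.4.1.1.
- Unless noted otherwise, first dose means the first dose in SP848: section 3.2.1.1.
- The visit and ECG schedule is in the protocol: section 2.4.2.

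**Cases**
1. *Direct enroller, unscheduled ECG after first dose and before the first post-dose scheduled visit.* The preceding scheduled visit is pre-dose. Its readings belong to Baseline, so it is not a post-Baseline visit. The abnormality is treatment-emergent but has no by-visit entry.
2. *As case 1, but this is the participant's last ECG in the Treatment Period.* It is the Last Visit value and is counted there.
3. *As case 1, but the abnormality is present again at a later ECG.* It was not met at Baseline, so the participant is counted at the later visit.
4. *Direct enroller, unscheduled ECG after at least one post-dose scheduled visit.* The receiving visit is post-Baseline and the abnormality is counted, although under a visit earlier than the one at which it was seen.
5. *Rollover participant, Baseline from the original study (section 3.3).* SP848 entry is already post-Baseline and has an entry, so nothing is lost.
6. *Rollover participant, pre-dose in section 8.4.2 read with the default in section 3.2.1.1.* Readings before the first SP848 dose become Baseline, and the gap of case 1 reappears. Section 8.4.2 does not say which reading applies.

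**Size**
The expected number missed would be N × P(unscheduled ECG in the gap) × P(it meets a Table 8-2 criterion not met at Baseline) × P(it is neither the Last Visit value nor repeated later). Only N can be approached from the SAP. Section 2.5 plans about 100 + 46 + 60 = 206 direct enrollers among about 400 participants. None of the three probabilities is given, and the length of the gap depends on the protocol's schedule. No count can be derived.

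**The case against.** The strongest reply is that this is one possible empty cell in a descriptive table. Titration visits are scheduled, so the gap closes at the first post-dose visit. A lasting abnormality is picked up later, and an abnormality on the final ECG is picked up at Last Visit. Section 8.4.2 lists all ECG values for all participants, lists separately those meeting any criterion, and lists clinically significant findings after the first dose. All of this is right, and it limits the point to abnormalities that are transient and not final. It does not close the gap: a listing is not a count, and the table would still understate the number with a treatment-emergent abnormality.

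Three stronger readings are tempting, but the SAP does not support them.
- *A reader might infer that participants counted at a visit could fall outside its denominator, because nothing requires an ECG at the receiving visit.* The sentence beginning "Percentages will be relative to the number of study participants with an" belongs to a different table, the investigator's normal/abnormal classification. No denominator is stated for the treatment-emergent table, and section 3.1 leaves denominators to the purpose of the analysis. The proviso about the preceding visit can also be read as presupposing an ECG there.
- *A reader might want every unscheduled abnormality mapped forward, as section 3.2.3 does for early-termination assessments, which "will be assigned to the next scheduled visit, for which the corresponding assessment is scheduled".* The analogy is weak. An early-termination assessment fills a scheduled slot that has no ECG of its own, whereas the visit after an unscheduled ECG normally has one, which may be normal. Backward or forward attribution is a convention; only the pre-dose receiving visit is a defect.
- *A reader might put a number on the participants lost.* Any such number would need rates that the SAP does not contain and would have to allow for recurrence.

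**Conclusion.** The point holds in a narrow form. For direct enrollers, a treatment-emergent ECG abnormality seen only at an unscheduled visit between first dose and the first post-dose scheduled visit is missing from the by-visit table, unless it is the Last Visit value or recurs at a later ECG. For rollover participants this holds only if pre-dose in section 8.4.2 refers to the first SP848 dose. It would be wrong to infer that all abnormalities early in treatment disappear, or that any finding goes unreported. The effect is probably small and cannot be estimated from the SAP. The conclusion assumes that the rule is programmed as written and that no separate any-time summary exists outside the SAP text. It is worth correcting because the written rule gives a wrong count in the only planned summary of Table 8-2 abnormalities, and the repair is cheap.

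**What to change.** Make two changes in section 8.4.2.

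(a) Add after the assignment rule: 'An abnormality seen at an unscheduled visit after the first dose of LCM is never summarized under a pre-dose visit; where the preceding scheduled visit is pre-dose, it is assigned to the first post-dose scheduled visit.' Leave the rule unchanged otherwise.

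(b) Add a row to the treatment-emergent table: 'Any time during the Treatment Period (scheduled or unscheduled)', with participants having at least one post-Baseline ECG as denominator.

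A short clause saying which study's first dose pre-dose refers to for rollover participants would also settle whether they are affected.

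The cost is a few lines of SAP text, a small change to the visit-assignment program and one extra table row. No new data are needed. The downside is that, in the edge case, an abnormality is shown at a visit slightly later than it occurred.

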**Table 8–2: ECG abnormality criteria**

Parameter	Age Range	Abnormality Criteria
QT interval (ms)	1m - <12y	≥500
	≥12y	≥500 or ≥60ms increase from Baseline
QTc(F) (ms)	<6m	>490, or >15% increase from Baseline
	6m - <3y	>440, or >15% increase from Baseline
	3y - <12y	>440, or >15% increase from Baseline
	≥12y - <17y	>440, or >15% increase from Baseline
	≥17y	≥500 or ≥60ms increase from Baseline
QTc(B) (ms)	<6m	>490, or >15% increase from Baseline
	6m - <3y	>450, or >15% increase from Baseline
	3y - <12y	>450, or >15% increase from Baseline
	≥12y - <17y	>450, or >15% increase from Baseline
	≥17y	≥500 or ≥60ms increase from Baseline
PR interval (ms)	<6m	>150, or ≥25% increase from Baseline
	6m - <3y	>170, or ≥25% increase from Baseline
	3y - <12y	>180, or ≥25% increase from Baseline

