**Table 8–2: ECG abnormality criteria**

Parameter	Age Range	Abnormality Criteria
	≥12y - <17y	>200, or ≥25% increase from Baseline
	≥17y	Treatment-emergent value >200, >220, >250
QRS interval (ms)	<6m	>90, or ≥25% increase from Baseline
	6m - <3y	>90, or ≥25% increase from Baseline
	3y - <12y	>100, or ≥25% increase from Baseline
	≥12y - <17y	≥110, or ≥25% increase from Baseline
	≥17y	Treatment-emergent value ≥100, >120, >140
Heart rate (bpm)	<6m	<100, >180
	6m - <3y	<90, >150
	3y - <12y	<60, >130
	≥12y	<50, >120

Abbreviations: bpm=beats per minute; m=months; ms=milliseconds; QTc=corrected QT interval; y=years. A month is defined as 28 days; a year is defined as 365.25 days.

A subject data listing will be provided that identifies study participants with a clinically significant finding after the first dose of LCM for each type of ECG abnormality.

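### SAP Section 8.4.2: applied cell by cell, the treatment-emergent ECG rule drops qualifying QTc, PR and QRS increases in children under 17 who are already above the absolute limit at Baseline

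*SAP*

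**What the plan says.** SAP Section 8.4.2 plans the number and percentage of participants with treatment-emergent ECG abnormalities at each post-Baseline visit and at Last Visit. To qualify, a participant must meet the criteria after Baseline, during the Treatment Period, "and not meeting the same criteria during Baseline". Age at the visit decides which criteria apply, and increases are measured from the Baseline value, which is the mean of the interpretable pre-dose readings.

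Table 8–2 supplies the criteria. Under 17 years, the QTc and conduction-interval cells each hold two limbs joined by *or*:

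- QTc(F), 6 months to under 17 years: ">440, or >15% increase from Baseline"
- QTc(B), the same ages: ">450, or >15% increase from Baseline"
- PR, 3 to under 12 years: ">180, or ≥25% increase from Baseline"; 12 to under 17 years: ">200, or ≥25% increase from Baseline"
- QRS, 3 to under 12 years: ">100, or ≥25% increase from Baseline"

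The remaining under-17 cells for these parameters have the same form with other limits. By contrast, the PR cell from 17 years lists graded limits with no relative limb: "Treatment-emergent value >200, >220, >250".

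The SAP does not say whether the Baseline condition applies to the whole cell or to each limb. It also does not say which age band's limit applies to the Baseline value once the child has moved to another band.

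**The concern.** The Baseline condition is there to keep a pre-existing abnormality from being counted as a treatment effect. It makes sense for an absolute limit. It does nothing useful for a relative increase, which is already measured against Baseline and cannot have been present there.

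Putting both limbs into one criterion lets the absolute limb disable the relative one. A child who starts just above the limit satisfies the cell at Baseline, so no later increase in that parameter can be treatment-emergent within that age band. These are the children who start with the longest intervals. The table affected is the SAP's threshold-based ECG outlier count, in a plan whose list of other significant adverse events (Table 12–3) opens with cardiac and ECG terms.

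There is also a reproducibility problem: two programmers could follow the same text and produce different counts.

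**Working it through.** The SAP states no figure on this point, so there is none to reproduce. The check applies the written rule in two ways.

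**Notation.** B = Baseline value, V = on-treatment value, A = absolute limit, r = relative limit (15% for QTc, 25% for PR and QRS).

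- Whole cell as one criterion: counted if (V exceeds A, or V/B − 1 meets r) and not (B exceeds A, or B/B − 1 meets r). Since B/B − 1 = 0, the Baseline condition reduces to B not exceeding A.
- Limb by limb: counted if (V exceeds A and B does not), or if V/B − 1 meets r.

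**Worked cases, age 8.**

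- QTcF 445 to 520 ms: 520/445 − 1 = 16.9%, above 15%. B = 445 exceeds 440. Whole cell: not counted. Limb by limb: counted.
- PR 185 to 235 ms: 235/185 − 1 = 27.0%, above 25%. B = 185 exceeds 180. Whole cell: not counted. Limb by limb: counted.

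**All cells.** Four parameters and four age bands under 17 give 16 cells. Each was tested with a Baseline 5 ms above its limit and increases of 10% to 50%, with the child staying in the same band. Read as one criterion, none of the 16 cells gave a count at any increase, including QTcF 445 to 668 ms, PR 185 to 278 ms and QRS 105 to 158 ms (each +50%). Read limb by limb, all 16 gave a count once the relative limb was met.

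**How large a rise is at stake.** The relative limb, starting from a Baseline at the limit, comes into play at the following values. A Baseline above the limit needs more.

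| Parameter | Age | A (ms) | A × (1 + r) (ms) |
|---|---|---|---|
| QTc(F) | <6 months | 490 | 490 × 1.15 = 563.5 |
| QTc(F) | 6 months to <17 years | 440 | 440 × 1.15 = 506 |
| QTc(B) | <6 months | 490 | 490 × 1.15 = 563.5 |
| QTc(B) | 6 months to <17 years | 450 | 450 × 1.15 = 517.5 |
| PR | <6 months | 150 | 150 × 1.25 = 187.5 |
| PR | 6 months to <3 years | 170 | 170 × 1.25 = 212.5 |
| PR | 3 to <12 years | 180 | 180 × 1.25 = 225 |
| PR | 12 to <17 years | 200 | 200 × 1.25 = 250 |
| QRS | <3 years (two bands) | 90 | 90 × 1.25 = 112.5 |
| QRS | 3 to <12 years | 100 | 100 × 1.25 = 125 |
| QRS | 12 to <17 years | 110 | 110 × 1.25 = 137.5 |

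**Change of age band.** Take PR 185 ms at Baseline under 12 years and 205 ms at a visit after the 12th birthday. The rise is 205/185 − 1 = 10.8%, so only the absolute limb matters. Judged against the visit-age limit (200), Baseline is within limits and the child is counted. Judged against the Baseline-age limit (180), Baseline is already abnormal and the child is not counted. Separating the limbs does not settle this case, so it needs its own rule. Likewise, QTcF 445 ms at 16 years and 500 ms at 17 is counted if Baseline is judged by the criteria that apply from 17 years (at least 500 ms, or an increase of at least 60 ms).

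**The case against.** The strongest reply is that the text already permits reading each limb on its own. Other cells of Table 8–2 plainly hold separate criteria: low and high heart rate share a cell, and the graded PR limits from 17 years would serve little purpose if exceeding the lowest at Baseline blocked the rest. Read that way throughout, the table works and both age-8 examples are counted. That reading is open, but the SAP never adopts it. The cells just named separate their thresholds with commas, whereas the under-17 cells use *or*, which a programmer would naturally code as one condition.

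A reader might infer that such a child can never be counted as having any treatment-emergent ECG abnormality. The documents do not support that. The exclusion is per parameter: a child with a long Baseline QTc can still count on PR, QRS, heart rate or the separate uncorrected QT row. A child who changes age band may also count, depending on the unstated Baseline-band rule.

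It is also true that the values are not hidden. Section 8.4.2 plans observed values and change from Baseline by visit, shifts in the investigator's assessment, a listing of all ECG values, and a listing for participants who meet any abnormality criterion. This limits the harm but does not replace the count: means dilute individual outliers, and listings give no incidence.

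**Conclusion.** The point holds as a badly fixed definition. On the natural reading of the cells, which nothing in the SAP excludes, a child under 17 who is above the absolute limit for QTc(F), QTc(B), PR or QRS at Baseline is not counted for that parameter while in the same age band, even when the rise satisfies the relative limb alone. For those children the treatment-emergent count can only be too low. If the limbs were in fact to be programmed separately, nothing is lost except that the SAP fails to say so.

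The size of the undercount cannot be given. The SAP reports no number of children above a limit at Baseline. An assumed Baseline distribution would give only the share exposed to the rule, not the missed events, which also require the rise itself: from 445 ms, a QTcF increase of more than 0.15 × 445 = 66.75 ms. A claim that ECG incidence is biased low across nearly the whole study population would therefore go beyond the evidence.

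A reader might also conclude that children should have the QTc limit of 500 ms or the graded PR limits used from 17 years. That is a preference about thresholds, not an error in this plan, and it forms no part of the point.

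**What to change.** In Section 8.4.2, state that each limb of a Table 8–2 cell is a separate criterion:

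- Absolute limit: treatment-emergent if exceeded on treatment and not exceeded at Baseline.
- Relative increase: treatment-emergent whenever met on treatment, whatever the Baseline level, because it cannot be met at Baseline.

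Also state which age band's absolute limit applies to the Baseline value when the child has changed band by the visit. Either choice can be programmed, but it must be written down.

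The cost is small: a few lines of SAP text, one extra flag per parameter in the analysis dataset, and slightly higher counts in the treatment-emergent table. No new data are needed.
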